Early Life Interventions for Childhood Growth and Development in Tanzania (ELICIT)

NCT03268902

5 February 2020

Statistical Analysis Plan for Primary and Secondary Outcomes (revised to reflect cognitive SAP)

1. Primary outcome, anthropometry secondary outcomes:

Developed and originally posted to ClinicalTrials.gov 5 February 2020

Page 2

2. Cognitive secondary outcomes:

Developed 13 January 2021; originally posted to ClinicalTrials.gov 27 April 2021

Page 5

I. Unblinding, outcomes, analysis populations, data cleaning

Timing of analysis plan and unblinding

This analysis plan is being posted prior to the termination of data collection (anticipated as early as 24 February, 2020). The study will remain blinded until the following conditions have been reached:

1. All 18-month anthropometry, 18-month cognitive testing, and 18-month questionnaires data collection are completed.
2. Database has been cleaned.
3. Primary analysis has been completed (blinded to intervention group), as described below.

Development of analysis code will be conducted on a dataset in which intervention groups have been randomly permuted. The final primary analysis will be conducted on true intervention groups blinded to which group corresponded to which intervention.

Outcomes

Primary outcome: Length-for-age z-score (LAZ) at 18 months

Secondary outcomes:

1. Weight-for-age z-score (WAZ) at 18 months
2. Head-circumference-for-age z-score (HCZ) at 18 months
3. Weight-for height z-score (WHZ) at 18 months
4. MUAC-for-age z-score at 18 months
5. Mortality
6. SAE's, overall and by category
7. AE's, overall and by category

Analysis populations

1. Intention to Treat (ITT): All children who were enrolled in the study and randomized.
2. Modified Intention to Treat (mITT): All children with a valid 18-month anthropometry measurement. The study was suspended by the Tanzanian regulatory agencies for a 9-week period, requiring some assessments to be performed up to 9 weeks outside the target date; these late measurements of the 18-month anthropometry outcomes related to the study suspension will be included.
3. Per-protocol: All children in the mITT group who met the additional criteria:
 - a. Breastfed (at least partially) through age 6 months
 - b. Received all doses of azithromycin
 - c. Received initial dose of each nitazoxanide course
 - d. Received no more than one drug administration (at 6, 9, 12, and 15 month visits) outside of the 14-day window around the target date
 - e. Received at least 50% of nicotinamide doses as measured by pill and sachet counting

Cleaning of anthropometry z-score data

Anthropometry z-scores were calculated using the zscorer v0.2 package based on the WHO child growth standards. Growth rates between each pair of adjacent measurements were then calculated. Any growth rates that were in the bottom 0.5% or the top 99.5% of the distribution for each age category were flagged. Absolute Z score differences between each measurement and its two flanking measurements were then used to determine which of the measurements was implausible. This implausible value was then coded as NA. Maternal heights will be cleaned by invalidation of values more than 6 standard deviations from the mean.

II. Analysis of Z-score outcomes (LAZ, WAZ, HCZ, WHZ, MUAC) -- mITT and per-protocol groups

ELICIT is a factorial study assessing two interventions (nicotinamide vs. placebo; antimicrobials vs. placebo). Our a priori plan was to analyze each intervention separately, and the study was powered for each primary effect. Thus, all of the processes described below to compare between intervention groups will first be done for nicotinamide (NIC-A vs. NIC-B)

and then for antimicrobials (ANTI-A vs. ANTI-B). This includes looking for baseline differences and choosing adjustment variables separately between NIC-A vs NIC-B and ANTI-A vs ANTI-B.

To determine if there are any synergistic effects of nicotinamide and antimicrobials, we will then include an interaction term between the two interventions in a linear regression model for the 18-month outcomes. If there is a statistically important interaction (defined as $p < 0.05$ from a Wald test), or a sizeable point estimate of the interaction term (defined as a difference of > 0.2 z-scores), we will report effects separately for NIC alone vs. control, ANTI alone vs. control, and NIC+ANTI vs. control.

Unadjusted analysis: Unadjusted analyses will be conducted by 2-sided t-test with $\alpha = 0.05$ and equal variance.

Adjusted analysis: We will also conduct an adjusted analysis to improve power and/or account for potential baseline differences as well as differences by loss-to-follow-up. Factors considered for the adjusted analysis include:

1. Enrollment measurement of outcome (e.g. LAZ, WAZ, HCZ, MUACZ)
2. Sex
3. Socioeconomic status (measured by the WAMI¹)
4. Maternal age, height, tribe, and education
5. Birth month
6. Hospital birth
7. Firstborn status
8. Ward of residence
9. Age when 18-month outcome was assessed

A priori, we will include the baseline measure of the corresponding anthropometry outcome in the adjusted analyses (NB: WAZ will be used for MUAC). Each of the remaining covariates above will be assessed in a bivariate analysis for the association with the 18-month outcome using linear regression. Those covariates with $p < 0.2$ or difference of 0.2 z-scores will be included in a multivariable analysis based on a linear regression model including the intervention group and each of the factors meeting the criteria above. For covariates that can be specified in different ways (e.g. using birth month as opposed to birth season), we will choose the model with the highest AIC. If point estimates and/or inference differ substantially between the unadjusted and adjusted analysis, we will rely on the adjusted analysis for the primary interpretation of results to ensure differences at 18-months are not explained by baseline differences.

For baseline characteristics with less than 5% missing data, we will single impute the mean values to retain all children in the adjusted analysis and retain comparability with the unadjusted analysis. In the adjusted analysis, for characteristics with $> 5\%$ missing data, we will consider multiple imputation if the covariate meets the criteria for inclusion in the model. We will also investigate whether missing outcome measurements (or lost-to-follow-up before 18 months) are associated with randomization arm or baseline characteristics. If so, we will use inverse-probability of censoring weighting to account for informative censoring.

Sensitivity analysis for mITT group: Unadjusted and adjusted sensitivity analyses will be performed in which children who have the 18-month outcome measurement taken outside the pre-specified measurement window will be excluded from the mITT group.

II. Adverse events, serious adverse events, and mortality – ITT group

For adverse events and serious adverse events, as well as for specific types of serious adverse events, unadjusted and adjusted incidence rate ratios comparing intervention arms will be calculated using Poisson or negative binomial regression as appropriate, with an offset term for the log of person time at risk.

For the analysis of the effects of antimicrobials, only events and person-time starting at six months (the first scheduled administration of antimicrobials) will be included.

For mortality, unadjusted analysis will be performed using a Kaplan-Meier survival analysis, using a log-rank test to test for differences between intervention arms. The adjusted analysis will be performed using a Cox proportional hazards model.

References

Introduction

The primary outcome for the ELICIT study was LAZ at 18 months. The analyses for that outcome and other anthropometry has been previously performed and the statistical analysis plan is publicly available (<https://clinicaltrials.gov/ct2/show/NCT03268902>). This analysis plan describes a separate outcome: primary cognitive outcomes at 18 months.

MDAT Outcomes

Primary: Development-for-age z score (DAZ) at 18 months (*dichotomous, <-1 SD (v-1.5, -2) v everyone else lowest v other quartiles of these scores*)

Overall DAZ at 18 months

Language DAZ at 18 months

Fine motor DAZ at 18 months

Secondary:

Overall DAZ at 24 months

Language DAZ at 24 months

Fine Motor at 24 months

Gross motor DAZ at 18 and 24 months

Social DAZ at 18 and 24 months

Analysis population

1. Intention to Treat (ITT): All children who were enrolled in the study and randomized
2. Modified Intention to Treat (mITT): All children with valid MDAT assessment at the end of the study (*target age 18 months*)
3. Per-protocol: All children in the mITT group who met the additional criteria:
 - a. Breastfed (at least partially) through age 6 months
 - b. Received all doses of azithromycin
 - c. Received initial doze of nitazoxanide course
 - d. Received no more than one drug administration (at 6, 9, 12, and 15 month visits) outside of the 14-day window around the target date
 - e. Received at least 50% of nicotinamide doses as measured by pill and sachet counting

Cleaning of MDAT z score data

Standardized MDAT z-scores were calculated using version 1.1 of the MDAT Scoring Application in Shiny. Internal validity checks with correlated answers were performed for each section (gross motor, fine motor, etc.).

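### The single per-protocol set requires adherence to both interventions, so each single-factor per-protocol comparison drops children who adhered to the product being tested

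*SAP*

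**What the plan says.** In the SAP's section I, under *Analysis populations*, there is one per-protocol set: "Per-protocol: All children in the mITT group who met the additional criteria". Five criteria follow, lettered a to e and applied together:

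- (a) breastfeeding, partial or full, up to 6 months of age;
- (b) "Received all doses of azithromycin";
- (c) the first dose in every nitazoxanide course;
- (d) at most one of the four drug administrations, due at 6, 9, 12 and 15 months, given more than the permitted 14-day margin from its target;
- (e) "Received at least 50% of nicotinamide doses as measured by pill and sachet counting".

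The z-score section is headed "Analysis of Z-score outcomes (LAZ, WAZ, HCZ, WHZ, MUAC) -- mITT and per-protocol groups", so this set is used for every z-score comparison described there. The same section says "Our a priori plan was to analyze each intervention separately" and runs each comparison first for NIC-A vs NIC-B and then for ANTI-A vs ANTI-B. Baseline checks and covariate choice are done separately for each factor. The per-protocol set is not.

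The cognitive part has the same structure: one joint a-to-e set, then the two factors analysed in turn.

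**The concern.** Criteria (b) and (c) concern the antimicrobials and (e) concerns nicotinamide. When all must be met, adherence to one factor's product decides who enters the per-protocol comparison of the other factor. A child who met the nicotinamide threshold but missed one azithromycin administration has relevant data on nicotinamide and is still removed. A child with every antimicrobial administration but under half of the nicotinamide doses is removed from the antimicrobial comparison.

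In an analysis at the margins of a factorial design, neither exclusion helps to answer the question asked. Each removes usable children, and each conditions the comparison on further behaviour observed after randomisation. At stake are the precision of the per-protocol estimates and how they are read. They would be taken as effects among adherers to the tested product, when they are effects among adherers to both products.

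**Working it through.** **Reading the definition against the comparisons.** Take *received* in (b), (c) and (e) to cover the allocated product, active or placebo. Assume each child below meets the criteria not mentioned.

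| Child | Fails | NIC-A vs NIC-B per-protocol | ANTI-A vs ANTI-B per-protocol |
|---|---|---|---|
| Met the nicotinamide threshold, missed one azithromycin dose | (b) | Excluded, though adherent to the tested product | Excluded for the tested product |
| All antimicrobial administrations, under 50% of nicotinamide doses | (e) | Excluded for the tested product | Excluded, though adherent to the tested product |

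One exclusion in each row has no bearing on the comparison it is removed from. This follows from the text alone.

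**Comparison with the rest of the SAP.** Elsewhere the plan tailors by factor. Covariates are chosen separately for each comparison, and the adverse-event section counts events and person-time for antimicrobials only from six months. The SAP gives no reason for leaving the per-protocol set untailored.

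**Size.** There is no planned figure to reproduce: the SAP gives no adherence rate, sample size, standard deviation or power figure. What follows is illustration with assumed inputs.

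Let q be the share of children adherent to the tested product who also meet the other factor's criteria. The joint set keeps a fraction q of the children that a factor-specific set would keep. With the same standard deviation and arm balance:

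SE ratio (joint / factor-specific) = 1/sqrt(q)

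| q (assumed) | Tested-product adherers dropped | SE ratio |
|---|---|---|
| 0.95 | 5% | 1.026 |
| 0.90 | 10% | 1.054 |
| 0.80 | 20% | 1.118 |
| 0.70 | 30% | 1.195 |

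**Dependence between the two adherences.** Suppose 80% of children meet each factor's criteria.

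- If the two are independent, 0.80 × 0.80 = 0.64 meet both. Then q = 0.64/0.80 = 0.80 and the SE rises by about 12%.
- With a correlation of 0.5, the share meeting both is 0.64 + 0.5 × 0.80 × 0.20 = 0.72. Then q = 0.72/0.80 = 0.90 and the SE rises by about 5%.

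Positive correlation is plausible, since the same families manage both products, so a figure based on independence probably errs on the high side.

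**The case against.** The strongest reply is that this is a choice and not a mistake. A set of children who followed the whole protocol is a recognised per-protocol definition in a factorial trial: it estimates each factor's effect where the other was also delivered as planned. It keeps the main-effect and interaction analyses on the same children. Analysing each intervention separately need not mean separate populations. This stands in part. It is a good reason to keep the joint set, above all for the interaction and the four-cell reporting. It does not justify making it the only set for the single-factor comparisons, and the SAP does not offer that argument.

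Three further objections stand and limit the point:

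- **The loss may be small.** Criterion (c) asks only for the first dose of each course, (d) tolerates one late or early administration, and (e) asks for half the doses. Only (b) is strict.
- **Bias is not shown.** In a blinded factorial trial there is no evident reason why adherence to the other factor's product should differ between the arms compared. What is established is extra exclusion and lost precision.
- **Criteria (a) and (d) cannot be assigned from the text.** Criterion (d) speaks only of drug administration at four visits. Those visits fit an antimicrobial schedule that starts at six months, but the SAP does not say whether nicotinamide was also handed out or given there.

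A reader might also infer that, because (b), (c) and (e) name only active products, children allocated to placebo could never qualify. The documents do not support this. The SAP describes both factors as placebo comparisons and keeps the study blinded until the primary analysis is done, on groups labelled A and B. A per-protocol set used to compare those groups can only refer to the allocated product. Adding the words *active or matching placebo* would be a clarification of wording and nothing more.

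**Conclusion.** The point holds as a cheap improvement limited to the per-protocol analyses. One joint set serves two comparisons that the plan treats as separate, so each loses children who adhered to the product under test. The mITT z-score analyses and the ITT safety and mortality analyses are unaffected.

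The size is unknown. The SE increases of about 5% (q = 0.9) and 12% (q = 0.8) rest wholly on assumed adherence. They should not be quoted as properties of this trial.

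**What to change.** Define a factor-specific per-protocol flag for each single-factor comparison, within the mITT group:

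- **Antimicrobial comparison:** criteria (b) and (c).
- **Nicotinamide comparison:** criterion (e).
- **Criteria (a) and (d):** the sponsor assigns each to the comparison or comparisons it concerns and states why.

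Keep the existing all-criteria set for the interaction analysis and the four-cell reporting, and as a sensitivity analysis for each single-factor comparison. No adherence threshold changes. Add *active or matching placebo* to (b), (c) and (e) for clarity. Use the same definitions in the cognitive part, where (c) at present leaves out the word *each*.

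The introduction to the cognitive part says the anthropometry analyses have already been performed. For those, report the factor-specific sets as an added analysis labelled as such, beside the per-protocol results already planned. Do the same for any cognitive per-protocol analysis already run.

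The cost is a change of wording, two more population flags and some extra output. The downside is that the two single-factor comparisons would rest on slightly different children, which a table of set sizes by arm would make visible.

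### The three cell contrasts are reported only when the same data show a large or significant interaction, so the single-product effects are exaggerated by selection and carry no error control or exploratory label

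*SAP*

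**What the plan says.** The rule is in the SAP, section II, Analysis of Z-score outcomes (LAZ, WAZ, HCZ, WHZ, MUAC), for the mITT and per-protocol groups.

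- The main analysis is at the margins: "Our a priori plan was to analyze each intervention separately, and the study was powered for each primary effect".
- An interaction term is then fitted, and a further report has two alternative triggers. The first is "If there is a statistically important interaction (defined as $p < 0.05$ from a Wald test"). The second is "or a sizeable point estimate of the interaction term (defined as a difference of > 0.2 z-scores"). Either is enough.
- When triggered, "we will report effects separately for NIC alone vs. control, ANTI alone vs. control, and NIC+ANTI vs. control".
- The interaction paragraph gives no level for the three contrasts, no adjustment for there being three, no allowance for the trigger, and no statement that they are exploratory. The nearest stated level is in the next paragraph: "Unadjusted analyses will be conducted by 2-sided t-test with $\alpha = 0.05$ and equal variance".

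The cognitive part of the SAP repeats the conditional reporting sentence for the MDAT scores, with a differently worded trigger.

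**The concern.** The trigger and the contrasts it releases are functions of the same four cell means. When the interaction is large by chance, the two single-product contrasts tend to be large as well, with the opposite sign. The reader sees them only in that situation. Ordinary p-values and 95% intervals take no account of this, so the single-product effects look bigger and more certain than they are.

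The rule covers 18-month LAZ, the primary outcome. In a trial where neither product does anything, a chance interaction could produce a table suggesting that one product alone helps or harms growth, with nothing in the SAP telling the reader to discount it.

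**Working it through.** **Inputs.** From the SAP: the two triggers (two-sided Wald p < 0.05, or an estimate above 0.2 z-scores) and three contrasts sharing one control cell. The 0.05 two-sided level is stated for the unadjusted analyses and is assumed here for each cell contrast. The SAP does not give the allocation (assumed 1:1:1:1), total N (200 to 2400 shown) or the SD of 18-month LAZ (0.9 to 1.2 shown). The 0.2 threshold is read as an absolute value. The SAP gives no error rate for this step, so there is no document figure to reproduce.

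**Correlations.** Let C, N, A and B be the means of the control, NIC-alone, ANTI-alone and combined cells, each with variance v.

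- Interaction I = B - N - A + C, variance 4v.
- NIC alone: N - C, variance 2v. Cov(I, N - C) = -v - v = -2v, so the correlation is -2/(2 x sqrt 2) = -0.71. ANTI alone is the same.
- NIC+ANTI: B - C. Cov(I, B - C) = v - v = 0, so the correlation is 0.

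A trigger on I therefore selects on both single-product contrasts and leaves the combined contrast alone.

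**First trigger only (p < 0.05), global null.** Simulation of 4,000,000 sets of four cell means, normal tests at 1.96. Neither N nor SD is needed.

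| Quantity | Without selection | Given the trigger |
|---|---|---|
| NIC alone nominally significant | 5% | 34% |
| ANTI alone nominally significant | 5% | 34% |
| NIC+ANTI nominally significant | 5% | 5% |
| At least one of the three | 12.5% | 57% |
| Mean absolute z, NIC alone | 0.80 | 1.66 |

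The joint rate is 0.050 x 0.570 = 0.0285, about 2.9% of null trials per outcome. Given the trigger, a nominal 95% interval for a single-product effect covers the true value of zero about 1 - 0.34 = 66% of the time.

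**Full either/or rule.** The standard error of I is 4 x SD / sqrt(N). At N = 400 and SD 1.0 it is 4/20 = 0.20, so the 0.2 trigger is met at one standard error and fires in 31.7% of null trials. Results at SD 1.0:

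| Total N | Triggered | At least one significant, given trigger | Joint |
|---|---|---|---|
| 400 | 31.7% | 25.2% | 8.0% |
| 800 | 15.7% | 36.7% | 5.8% |
| 1200 | 8.3% | 48.1% | 4.0% |
| 1600 and above | 5.0% | 57.0% | 2.9% |

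Over N 200 to 2400 and SD 0.9 to 1.2, the conditional rate runs from about 18% to 57% and the joint rate from about 10% down to 2.9%. The two move in opposite directions: a looser trigger dilutes each report but produces more reports. If only positive estimates above 0.2 counted, the conditional range would be about 21% to 57%.

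The second trigger adds nothing once 1.96 x 4 x SD / sqrt(N) falls below 0.2, that is N > 16 x SD² x (1.96/0.2)². This gives about 1245 at SD 0.9, 1537 at SD 1.0, 1859 at SD 1.1 and 2213 at SD 1.2.

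**Any nominal false finding on LAZ.** Two main effects alone: 9.7%. Adding triggered cell contrasts: 12.2% under the first trigger alone, 15.5% under the full rule at N = 400 and SD 1.0, and 16.0% at N = 200 and SD 1.2. If triggered contrasts replaced the main effects, the rate would be about 12% to 15%.

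**Would a multiplicity correction suffice?** No. Given p < 0.05 for the interaction, at least one contrast is still significant in 29.3% of reports with Bonferroni (0.05/3) and in 31.8% with a Dunnett-type critical value of 2.35.

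**The case against.** The strongest reply is that the SAP only reports these effects. It prescribes no test of them and declares no success on them. The marginal comparisons come first, are what the study was powered for, and do not depend on this step. All of that stands. A reader might infer that the primary conclusion is compromised or that a cell contrast could win the trial; the documents support neither.

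A reader might also take 57% as the rate for the plan, as if the contrasts followed only a significant interaction. The same sentence has the 0.2 route, so a non-significant interaction can also trigger the report. The 57% belongs to the p < 0.05 trigger and is the upper end for the full rule. It also conditions on an event that occurs in 5% of null trials, and the combined contrast is not inflated at all.

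On the remedy, showing three intervals every time means at least one excludes zero in about 12.5% of null trials, against 2.9% now under the first trigger. That is true, but it is the ordinary, known rate for three unselected intervals, and the label tells the reader how to take them. Adding the word exploratory while keeping the trigger would leave the reported estimates exaggerated. If a real interaction exists, its own estimate and interval still show it.

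**Conclusion.** The point holds as a defect in a conditional follow-up report, worth correcting because correction is cheap. The rule selects exaggerated single-product effects on the primary and other z-score outcomes and gives no warning.

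The finding about direction rests only on the four cells being of roughly equal size. The 57% also needs the global null and a nominal two-sided 5% reading of each contrast. The ranges for the full rule depend further on N and SD, which the SAP does not give, so no single figure describes the plan as written. The increase in any nominal false LAZ finding is about 2.5 percentage points at the low end (12.2 - 9.7) and about 6 at the high end (16.0 - 9.7), and it matters only if a cell contrast is read as a finding.

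**What to change.** In the interaction paragraph for the anthropometric outcomes, and in the matching sentence for the cognitive outcomes, replace the conditional reporting with:

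> The four cell means, the three contrasts against control and the interaction estimate will be reported with 95% confidence intervals for every z-score outcome whatever the interaction result; the cell contrasts are exploratory and carry no significance claims.

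Unconditional reporting removes the selection under either trigger, and the label deals with the three unadjusted contrasts. The marginal analyses stay as they are. The cost is one sentence in each of the two places and one extra table. The downside is that a cell contrast can no longer be claimed as significant by itself.

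### The SAP labels neither the t-test nor the adjusted model as the primary analysis of 18-month LAZ, and ranks them by an undefined difference judged once both results are known

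*SAP*

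**What the plan says.** Under the heading on timing and unblinding, the SAP lists as an unblinding condition: "Primary analysis has been completed (blinded to intervention group), as described below". The final run uses the true groups, with arm identity masked.

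Section II on the z-score outcomes then gives two analyses:

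- "Unadjusted analyses will be conducted by 2-sided t-test", at alpha 0.05 with equal variance.
- "We will also conduct an adjusted analysis to improve power" and to account for baseline imbalance and loss to follow-up. This is a linear regression that always contains the enrolment measure of the outcome, with other covariates chosen by a screening rule.

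One sentence ranks them: "If point estimates and/or inference differ substantially between the unadjusted and adjusted analysis, we will rely on the adjusted analysis for the primary interpretation". Its stated purpose is "to ensure differences at 18-months are not explained by baseline differences".

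The same section puts a number on a comparable judgement. The interaction is acted on if p < 0.05 or if there is "a sizeable point estimate of the interaction term (defined as a difference of > 0.2 z-scores".

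**The concern.** The unblinding condition refers to a primary analysis that the text below it does not identify. Order and wording suggest a t-test default with a one-way override to the adjusted model, but the SAP does not say so. Three things are open:

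- how large a difference is substantial;
- whether a change in significance is enough by itself;
- which result is the headline when the two do not differ.

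The override can be judged only after both results are known. Masked A/B labels hide which arm benefits. They do not hide whether a two-sided test is significant, so they do not remove the choice.

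At stake are the power of the primary comparison and the estimate and interval that represent it.

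**Working it through.** **The plan's own figure.** The only one that bears on this is the two-sided alpha of 0.05. A critical value of 1.960 gives 0.0500 for a single named test, so it reproduces.

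**Assumed inputs.** The SAP gives no sample size, SD or covariate R² (share of LAZ variance explained). Assumed: R² 0.2-0.5, N 600-1200, SD 1.0-1.1, t-test power 80%. The unadjusted standard error is 2·SD/√N, from 2·1.0/√1200 = 0.058 to 2·1.1/√600 = 0.090. The adjusted model is treated as fixed, so covariate screening is not counted.

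**Model.** In units of the unadjusted standard error, with e1 and e2 independent standard normal:

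- adjusted estimate = d + √(1−R²)·e1
- unadjusted estimate = adjusted estimate + √R²·e2
- d = 0 under the null; d = 1.960 + 0.842 = 2.80 for 80% t-test power

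**Step 1: the two analyses compared.** Adjusted power is Φ(2.80/√(1−R²) − 1.960). The t-test interval is 1/√(1−R²) times as wide as the adjusted one.

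| R² | Adjusted power | Width ratio | Agree on significance, effect present | Agree, null | Either significant, null |
|---|---|---|---|---|---|
| 0.2 | 0.880 | 1.118 | 0.890 | 0.958 | 0.071 |
| 0.3 | 0.918 | 1.195 | 0.861 | 0.949 | 0.076 |
| 0.4 | 0.951 | 1.291 | 0.836 | 0.941 | 0.080 |
| 0.5 | 0.977 | 1.414 | 0.817 | 0.934 | 0.083 |

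**Step 2: every change in significance counts.** The significance verdict is then always the adjusted model's: type I error 5.0%, power 88-98%. In the 82-89% of trials with an effect where the tests agree, the headline interval is still unspecified and could be 12-41% wider.

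**Step 3: other triggers, t-test leading otherwise** (simulation, 2,000,000 draws per R²).

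| Trigger for the adjusted model | Power | Type I error |
|---|---|---|
| p-values differ by > 0.05 | 0.861-0.971 | 0.050 |
| p-values differ by > 0.10 | 0.826-0.901 | 0.050 |
| Estimates only, > 0.05 z | 0.809-0.912 | at most 0.050 |
| Estimates only, > 0.1 z | 0.800-0.842 | at most 0.050 |
| Estimates only, > 0.2 z | 0.800-0.801 | at most 0.050 |

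The 0.2 z threshold is borrowed from the interaction paragraph; the SAP does not set it for this rule. Triggers based on relative change in the estimate were also tried. The highest type I error was 5.1%, for a 50% change at R² 0.2.

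**Step 4: selective use.** If whichever test is significant were allowed to lead, type I error per intervention would be the last column of the first table, 7.1-8.3%.

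**The case against.** The strongest reply is that a rule exists and points one way. The t-test comes first, alpha is stated only there, the adjusted analysis is an addition, and any substantial difference in inference moves the lead to the adjusted model. On that reading only one adverb is undefined. Where nothing differs substantially, the conclusion is the same whichever leads. This largely stands: it limits the consequence, but it does not supply the threshold or name the default.

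It is also fair that the estimate-gap-only reading, which gives the largest power loss, sets aside the rule's mention of inference. The 80% figure is therefore the far end of the range. A p-value gap of 0.05 costs only about 1 to 2 points against the adjusted model.

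A reader might infer that the wording inflates type I error to 7-8%. The document does not support that. Such a rate needs a t-test that alone is significant to be kept selectively, against the rule's stated direction, and nothing shows that this happened. Nor can one claim that no consistent reading exceeds 5%, since one tested reading gave 5.1%.

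Masked labels are a real safeguard against favouring a named arm, though not against favouring a significant result.

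**Conclusion.** The point holds in a limited form. The primary analysis of LAZ is not identified, and the only ranking rule has no threshold and no stated default. The practical cost is in power and precision: depending on the reading, power runs from the t-test's 80% to the adjusted model's 88-98%, and the reported interval could be 12-41% wider than it need be. Meaningful type I error inflation is not shown. These sizes rest on the assumed R² of 0.2-0.5, t-test power of 80% and a fixed adjusted model; the estimate-gap results also rest on the assumed N and SD. The case for a change is that naming one analysis costs almost nothing. Covariate selection, age at assessment and the cognitive plan are separate questions.

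**What to change.** State that the adjusted linear model, always including enrolment LAZ as the SAP already requires, is the primary analysis of 18-month LAZ for both interventions whatever the t-test shows. Make the t-test supportive.

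The Introduction to the cognitive plan says that the LAZ analyses have already been performed, so this cannot count as pre-specified. Therefore:

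- label it as a post-analysis change;
- keep the posted rule on record;
- report both results in full, with intervals, for each intervention;
- state which result led the interpretation and on what ground.

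The last two items can still inform the reader even if the SAP is not revised. The cost is wording and reporting only; no new data are needed.
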